## **5.2 AEs coding/grading**

AEs are coded using the MedDRA terminology. The latest version of MedDRA will be used and will be specified in the footnote of relevant output.

AEs grade are assessed by investigators and captured on the AE CRF based on three levels: mild, moderate, and severe.

## **5.3 Laboratory parameters derivations**

Not applicable.

## **5.4 Visit windows**

In general, if two consecutive visits  $V_t$  and  $V_s$  are  $x$  days apart, the upper limit of the visit window for  $V_t$  will be  $V_t+x/2$  and the lower limit for the visit  $V_s$  will be  $V_s-x/2 + 1$  (if  $x$  is even). The algorithm needs to ensure that visit windows are not overlapping and that there are no gaps, such that each assessment can be uniquely allocated to one visit window.

Both scheduled and unscheduled assessments will be considered.

In case of competing assessments within a visit window:

- For efficacy parameters: the assessment value closest to the scheduled visit day will be used. In case of equal distances, the earliest assessment value will be used.
- For safety parameters: the worst assessment value within the visit window will be used (see [Section 5.4](#)). If more than one assessments are equally worst, the one closer to visit window will be used.

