- Increased serum neurofilament light chain (sNfL) levels observed in more than half of the participants after 9 weeks on treatment
- Decreased amplitude in the sural nerve (SNAP) compared to baseline in the 3 participants with both an increase in sNfL and decreased or absent DTRs
- Paresthesia in the lower extremities was reported by two participants. One resolved on treatment within 5 days and one led to early treatment discontinuation and subsequently resolved.

In this communication:

Participants that were actively taking study treatment at the time were instructed to stop the study treatment immediately and to return to the site for an on-site visit no later than 7 business days after being informed of the USM. The USM letter provided details on the assessments to be conducted during that visit. Subsequent to this on-site visit participants were to continue to adhere to their monthly visit evaluation schedule for on-site visits as per protocol (e.g., Week 9, 13, 17, 21, 25 etc.) until further notice. During these visits, all scheduled assessments were to be performed as per protocol with the following exceptions:

- Study drug should no longer be taken by participants
- PK [REDACTED] including mHTT/HTT (plasma [REDACTED]) [REDACTED] should only be collected up to 6 weeks after the last dose of study drug. The 0-Hour timepoint (pre-dose in the protocol pre-USM) is the only required timepoint for collection.
- No additional lumbar puncture will be scheduled thereafter unless deemed necessary by the investigator.
- Follow-up Nerve Conduction Study (NCS) evaluation may be required on a case-by-case basis, in consultation with the DMC.

Participants that had already permanently discontinued study treatment and had scheduled an End of Treatment (EOT) and/or follow up assessments at the time of this USM were to continue the previously agreed upon schedule of assessments as per discussions between investigator and Sponsor.

Subsequently a **Follow-up IN (24-Oct-2022)** was sent to sites to provide an update on activities related to the ongoing study following the initial communication on 05-Aug-2022. No new changes were implemented as the purpose was to remind of the above schedule of assessments exceptions.

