8.4.2 Cardiac assessments

Electrocardiogram (ECG)

As per USM: Refer to [Table 8-5 for schedule of ECG assessments. Participants do not require to be fasting prior to the ECG.](#)

ECGs must be recorded after 10 minutes rest in the supine position to ensure a stable BL, according to the ECG Investigator Manual. The Fridericia QT correction formula (QTcF) should be used for clinical decisions.

TriPLICATE 12-lead resting ECGs are to be collected, with ECG machines as supplied by central ECG vendor, at all timepoints pre-specified in the visit and assessment schedule and should be performed with a 2-4 minutes interval between each ECG. Details on the triplicate ECG collection procedure and its specific requirements and restrictions for the participant are provided in an ECG Investigator Manual. Specific visits will require fasting prior to pre-dose ECGs as specified in [Table 8-8](#), and in [Section 6.7.2](#). For PK sampling timepoints, please see [Appendix 16.3](#).

Table 8-8 Central ECG Collection Plan

Period	Visit Name	Days	Timepoint	Timing of Triplicate ECGs
Screening	Screening	-42 to -7	-	Anytime
Baseline	Baseline	-6 to -1	-	Anytime
DRF	Wk 1	1	0 hr	Pre-dose after 4 hr fasting
DRF	Wk 1	1	4 hr	Post-dose
DRF	Wk 1	1	12 hr	Post-dose after 4 hr fasting
DRF	Wk 2	8	-	Pre-dose
DRF	Wk 3	15	-	Pre-dose
DRF	Wk 5	29	-	Pre-dose
DRF	Wk 9	57	0 hr	Pre-dose after 4 hr fasting
DRF	Wk 9	57	4 hr	Post-dose
DRF	Wk 9	57	12 hr	Post-dose after 4 hr fasting
DRF	Wk 13	85	-	Pre-dose
DRF	Wk 17	113	0	Pre-dose
BE & OLE	Wk 21 until EOT OLE	141 to EOT OLE	-	Pre-dose

For any ECGs with participant safety concerns, the Investigator should treat based on standard of care.

In the event that a clinically significant ECG abnormality is identified at the site at the time of ECG collection (e.g. severe arrhythmia, conduction abnormality of QTcF >500 msec), an expedited review by the central reader may be requested if applicable, and the ECG should be repeated to confirm the diagnosis. If the participant is hemodynamically compromised, the Investigator or a medically qualified person must initiate appropriate safety procedures without delay (for example cardioversion).

Clinically significant abnormalities must be recorded on the eCRF as either medical history/current medical conditions or adverse events as appropriate.

Echocardiogram with Global Longitudinal Strain (GLS)

Echocardiogram with GLS is no longer required per the USM follow-up notification dated 06-Dec-2022.

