### Visit windows

Visit-windows will be used for by visit summary tables. For any assessment, there are the protocol defined scheduled visits around which visit windows were created to cover the complete range of days within the study. When visit windows are used, all visits will be re-aligned, i.e., they will be mapped into one of the visit windows.

However, for figures that involves individual trajectory (NFL, volMRI, mHTT) and for reports related (regarding worsening and recovery) to Neuro exam or Neuropathy questionnaire, an additional analysis visit based on actual analysis time (in weeks) instead of mapped windows will be used. This will be derived as ceiling of  $\{ \text{ADY}/7 \}$ . ADY is study day defined in [Section 2.1.1](#).

Details on calculation of visit windows based on the protocol will be provided in [Section 5.4](#).

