**Table 5-4      Visit windows for echocardiogram**

Label	Start day	Target day	End day
Baseline	See baseline assessment of the Study ( Section 2.1.1 , baseline definition)		
Wk 2			
Wk 3			
Wk 5	2	29	57
Wk 9			
Wk 13	58	85	113
Wk 17			
Wk 21	114	141	169
Wk 25			
Wk 29	170	197	225
Wk 33			
Wk 37			
Wk 41			
Wk 45			
Wk 49			
Wk 53	338	365	393
Wk 57			
Wk 61			
Wk 65			
Wk 69			

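### As printed, SAP Table 5-4 has no echocardiogram window for Days 226–337, so a Week 37 or Week 45 echo would have no row in the by-visit LVEF and GLS tables

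*SAP*

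**What the plan says.** SAP Section 2.1.1 states that "Visit-windows will be used for by visit summary tables" and that, around the scheduled visits, "visit windows were created to cover the complete range of days within the study". Section 5.4 gives a midpoint rule for the limits, applies it to scheduled and unscheduled assessments alike, and adds: "The algorithm needs to ensure that visit windows are not overlapping and that there are no gaps".

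The table titled "Visit windows for echocardiogram" (Table 5-4) prints days for five visits only: Weeks 5, 13, 21, 29 and 53. The row "Wk 29 170 197 225" is the last before the break. The labels for Weeks 33 to 49 and 57 to 69 are printed without days.

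Protocol Table 8-2 schedules blinded-extension echoes at Weeks 21, 29, 37, 45 and 53. After the first safety notice of 05-Aug-2022 dosing stopped but visits went on. The Amendment 02 rationale says "During these visits, all scheduled assessments were to be performed as per protocol with the following exceptions", and echocardiography is not among those exceptions. Protocol Section 8.4.2 then records: "Echocardiogram with GLS is no longer required per the USM follow-up notification dated 06-Dec-2022".

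SAP Section 2.7.4.1 plans by-visit descriptive statistics for LVEF and GLS, a count of participants with notable values at any post-baseline visit, and a listing restricted to participants with notable values. Table 5-14 gives a notable criterion for LVEF only.

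**The concern.** A by-visit table can show only what a window captures. If Table 5-4 is programmed as printed, a Week 37, Week 45 or unscheduled echo on Days 226–337 belongs to no visit and drops out of the LVEF and GLS summaries.

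Anyone who reached those days before 06-Dec-2022 was randomised early, so these participants had the longest possible treatment and the latest echoes on the original schedule. Protocol Table 4-2 names cardiovascular effects as a potential risk, so off-drug LVEF and GLS follow-up is worth showing completely. GLS is the more exposed of the two because its only planned summary is the by-visit table.

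**Working it through.** **1. Reproduce the printed windows.** For consecutive visits at days Vt and Vs, x days apart, the SAP rule gives upper limit of Vt = Vt + x/2 and lower limit of Vs = Vs − x/2 + 1. The targets are the protocol's echo days; Day 421 (Week 61) is the next one, in Protocol Table 8-3. All are 56 days apart, so x/2 = 28. The first start, Day 2, is taken from the SAP.

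| Visit (target day) | By the rule | Printed |
|---|---|---|
| Week 5 (29) | 2 to 29 + 28 = 57 | 2–57 |
| Week 13 (85) | 58–113 | 58–113 |
| Week 21 (141) | 114–169 | 114–169 |
| Week 29 (197) | 170–225 | 170–225 |
| Week 37 (253) | 253 − 28 + 1 = 226 to 281 | no days |
| Week 45 (309) | 282 to 309 + 28 = 337 | no days |
| Week 53 (365) | 338–393 | 338–393 |

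All five printed windows reproduce.

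**2. Size of the gap.** 337 − 226 + 1 = 112 days, exactly two 56-day windows.

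**3. Is it a deliberate omission?** If Weeks 37 and 45 had been dropped, Weeks 29 and 53 would be neighbours with x = 365 − 197 = 168. The rule would then give Week 29 = 170 to 197 + 84 = 281, and Week 53 from 365 − 84 + 1 = 282. The printed 225 and 338 arise only if Weeks 37 and 45 lie between them.

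**4. Could an echo fall there?** Day d is reached by 06-Dec-2022 if Day 1 is no later than 06-Dec-2022 minus (d − 1) days. Possible dosing time runs to the last dose in the study, 08-Aug-2022.

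| Study day | Latest Day 1 | Possible dosing time |
|---|---|---|
| 226 | 25-Apr-2022 | 106 days (about 15 weeks) |
| 253 (Week 37) | 29-Mar-2022 | 133 days (19 weeks) |
| 309 (Week 45) | 01-Feb-2022 | 189 days (27 weeks) |

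The SAP document history places first patient first visit after 30-Nov-2021, so such starts are possible.

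**5. On or off drug?** SAP Section 2.1.1 calls an assessment off treatment from last dose + 14 days, at the latest 22-Aug-2022 here. A Day 253 echo is off drug whenever Day 1 is 13-Dec-2021 or later (22-Aug-2022 minus 252 days). With at least 7 days of screening, Day 1 cannot precede about 07-Dec-2021, so nearly all such echoes are off drug.

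**6. After Day 393.** A Day 1 as early as 30-Nov-2021 would make 06-Dec-2022 Day 372; with 7 days of screening it is Day 365. No echo required before the stop can fall after Day 393.

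**The case against.** The strongest reply is that the cells may simply have been lost when the PDF was read. The labels for Weeks 37 and 45 are there, and the neighbouring limits are just what filled rows would produce. That stands, and only the original page can settle it. It is also said that a programmer could apply the Section 5.4 rule without an amendment. That stands only in part: as step 3 shows, the rule gives different windows depending on whether Weeks 37 and 45 count as visits, and the printed table conflicts with it either way.

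Second, the affected echoes may be few or none. Protocol Section 8 after the amendment keeps the original schedule only to Week 29 and then uses Weeks 33, 53 and 69. Protocol Section 4.4, in the amendment of 30-Jan-2023, still treats completion of Week 33 by about 70% of Cohort 1 as a future event. A reader might infer from the safety notice that some participants had passed Week 33 by December. The text only provides for placebo participants who might have done so, and passing Week 33 is not reaching Week 37.

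Third, a reader might infer that the main off-drug cardiac data are lost. The documents do not support that. For Day 1 on 29-Mar-2022, the Week 29 echo falls on 11-Oct-2022, about nine weeks after the last possible dose, and is mapped. Any Day 1 from 07-Feb-2022 puts the Week 29 target off treatment. ECG, troponin and NTproBNP windows run through Week 69.

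Fourth, the count of notable values at any post-baseline visit does not depend on windows. This covers LVEF, but not GLS. Protocol Section 8.4.2 defines a relevant GLS change, but SAP Table 5-14 as printed has no GLS criterion, so a GLS value in the gap is listed only if that participant also has a notable LVEF.

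**Conclusion.** The inconsistency is real as printed: 112 days without an echocardiogram window, against the SAP's own no-gap rule and across two scheduled echo visits. Any echo on those days is absent from the by-visit LVEF and GLS tables, and for GLS from every planned echo summary. Both arms are affected. The loss is confined to descriptive tables in an abbreviated report, and the number of echoes cannot be worked out because the documents give neither enrolment dates nor counts.

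This rests on two assumptions: that the blank cells are blank in the original, and that the LVEF limit in Table 5-14, printed with a minus sign, is read as the 50% threshold of Protocol Section 8.4.2.

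A stronger reading would add the absence of a window after Day 393 as a second loss. The documents do not support that: nobody could be past about Day 372 when echo ceased to be required, and Protocol Table 8-5 has no echo row. Only unscheduled or non-required echoes could land there. Nor is Table 5-4 alone in stopping early: the ophthalmology windows in Table 5-5 end at Day 449.

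**What to change.** Check the original Table 5-4 first. If the cells are filled there, nothing needs changing for Days 226–337. If they are blank, add Week 37 = Days 226–281 (target 253) and Week 45 = Days 282–337 (target 309). The five existing windows stay as they are. The cost is two table rows and the matching lines in the visit-mapping program.

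For echoes after Day 393, either state that they are only listed, and list them whether or not they are notable, or give them a separately labelled late window. Running Week 53 to the end of study is less attractive: Section 5.4 takes the worst safety value within a window, so a late unscheduled echo could be reported as the Week 53 result.

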**Note that NFL (both serum and CSF) will be considered as safety parameters (the higher the worse).**

For tables displaying the worst-case scenario for safety assessment, all assessments within a visit window will be used to identify the worst.

Listings will include all assessments, sorted by date of assessment, flagging unscheduled visits. The listings will flag to indicate the assessment's inclusion in the analysis.

In the below tables, the end of Core period is defined as the day of last assessment for Core period and the end of OLE is defined as the day of last assessment for OLE.

**Table 5-2      Visit windows for Neurological Exams, nerve conduction studies, weight, urinalysis, C-SSRS**

Label	Start day	Target day	End day
Baseline	See baseline assessment of the Study ( Section 2.1.1 , baseline definition)		
Wk 1			
Wk 2	2	8	11
Wk 3	12	15	22
Wk 5	23	29	43
Wk 9	44	57	71
Wk 13	72	85	99
Wk 17	100	113	127
Wk 21	128	141	155
Wk 25	156	169	183
Wk 29	184	197	211
Wk 33	212	225	239
Wk 37	240	253	267
Wk 41	268	281	295
Wk 45	296	309	323
Wk 49	324	337	351
Wk 53	352	365	421
Wk 69	422	477	until end of study

**Table 5-3      Visit window for vital Signs, ECG, Hematology, chemistry, NTproBNP, Troponin**

Same as [Table 5-2](#) except the beginning phase:

Label	Start day	Target day	End day
Baseline	See baseline assessment of the Study ( Section 2.1.1 , baseline definition)		
Wk 1	1 (planned post-dose)	1	4
Wk 2	5	8	11
Wk 3	12	15	22
....			

**Table 5-4      Visit windows for echocardiogram**

Label	Start day	Target day	End day
Baseline	See baseline assessment of the Study ( Section 2.1.1 , baseline definition)		
Wk 2			
Wk 3			
Wk 5	2	29	57
Wk 9			
Wk 13	58	85	113
Wk 17			
Wk 21	114	141	169
Wk 25			
Wk 29	170	197	225
Wk 33			
Wk 37			
Wk 41			
Wk 45			
Wk 49			
Wk 53	338	365	393
Wk 57			
Wk 61			
Wk 65			
Wk 69			

**Table 5-5      Visit windows for ophthalmologic examination**

[figure not shown]
Label	Start day	Target day	End day
Baseline	See baseline assessment of the Study ( Section 2.1.1 , baseline definition)		
Wk 2			
Wk 3			
Wk 5			
Wk 9			
Wk 13	2	85	169
Wk 17			
Wk 21			
Wk 25			
Wk 29			
Wk 33			
Wk 37	170	253	309
Wk 41			
Wk 45			
Wk 49			
Wk 53	310	365	449

Label	Start day	Target day	End day
Wk 57			
Wk 61			
Wk 65			
Wk 69			

**Table 5-6**

**Visit windows for UHDRS scores (TFC, TMS, IS, [REDACTED]), [REDACTED] and brain MRI**

Label	Start day	Target day	End day
Baseline			See baseline assessment of the Study ( Section 2.1.1 , baseline definition)
Wk 2			
Wk 3			
Wk 5			
Wk 9			
Wk 13			
Wk 17	2	113	169
Wk 21			
Wk 25			
Wk 29			
Wk 33	170	225	295
Wk 37			
Wk 41			
Wk 45			
Wk 49			
Wk 53	296	365	421
Wk 57			
Wk 61			
Wk 65			
Wk 69	422	477	until end of study

**Table 5-8      Visit windows for biomarker collected via lumbar puncture**  
([REDACTED] Nfl [REDACTED])

Label	Start day	Target day	End day
Baseline			
	See baseline assessment of the Study ( Section 2.1.1 , baseline definition)		
Wk 1			
Wk 2			
Wk 3			
Wk 5			
Wk 9	2	57	85
Wk 13			
Wk 17	86	113	169
Wk 21			
Wk 25			
Wk 29			
Wk 33	170	225	295
Wk 37			
Wk 41			
Wk 45			
Wk 49			
Wk 53	296	365	421
Wk 57			
Wk 61			
Wk 65			

Label	Start day	Target day	End day
Wk 69	422	477	until end of study

## 5.5 Notable and abnormality criteria

Please notice that in the below tables, we always used 'baseline' for clarity. For the OLE summaries, please replace by Baseline-Ext, as appropriate.

**Table 5-9 Clinically notable criteria for vital signs**

Vital Sign Variable	Notable Criteria
Pulse Rate (beats/min)	> 120bpm or Increase of $\geq 15$ bpm from baseline or < 50bpm or Decrease of $\geq 15$ bpm from baseline
Systolic BP (mmHg)	>180 mm Hg or Increase of $\geq 20$ mm Hg from baseline Or < 90 mm Hg or Decrease of $\geq 20$ mm Hg from baseline
Diastolic BP (mmHg)	> 105 mmHg or Increase of $\geq 15$ mm Hg from baseline Or < 50 mmHg or Decrease of $\geq 15$ mm Hg from baseline
Body weight (kg)	Decrease $\geq 7\%$ from baseline weight Increase $\geq 7\%$ from baseline weight
Body Temperature (°C)	High: $>= 38$ °C

**Table 5-10 Abnormal ranges for ECG**

ECG Parameter	Abnormality Flags	
	Lower bound	Upper bound
Notable value		
HR	<50 bpm or $\leq -15$ bpm change from baseline	>120 bpm or $\geq 15$ bpm change from baseline
RR Interval	< 600 msec	> 1200 msec
PR interval	< 120 msec	> 200 msec
QRS Interval	< 60 msec	> 109 msec
QT Interval	< 320 msec	> 450 msec
QTcF Interval (Fridericia's correction)	< 320 msec	> 450 msec
Notable relative change from previous visit		
QTcF Interval (Fridericia's correction)	$\leq -20\%$ ;	$\geq 20\%$

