Concentration-response analyses revealed a positive correlation between the branaplam plasma concentration and the placebo-adjusted mean change from baseline in QTcF ($\Delta\Delta$ QTcF),

characterized by the equation: $\Delta\Delta QTcF$ (ms) = 0.04912 x LMI070 plasma concentration (ng/mL). The estimated mean $\Delta\Delta QTcF$ exceeded 10 ms in the investigated exposure range while it appeared to be less than 5 ms at the Cmax of the 210 mg dose. In addition, a trend of mean $\Delta\Delta HR$ increase of approximately 2 bpm was observed in the investigated exposure range, which was not considered to be of clinical relevance.

There was no apparent trend of clinical relevance in the concentration-response analyses of other ECG variables. Categorical outlier analyses revealed a single treatment-emergent new $QTcF > 450$ ms and an increase of $QTcF$ from baseline > 30 ms at the 420-mg dose. There were no treatment-emergent $QTcF$ values > 480 ms, no increase in $QTcF$ or QT from baseline > 60 ms and no ECG events or imbalance of clinical relevance for other ECG variables.

Concentration-response analyses of branaplam plasma concentration and the placebo-adjusted mean change from baseline in systolic and diastolic blood pressure showed no clear correlation (slopes of prediction lines for the mean effect were 0.00404 and – 0.00714, respectively).

The potential cardiovascular risks will be mitigated and monitored by following the appropriate exclusion criteria, adherence to protocol specified prohibited medications ([Section 6.2.2](#)), history and physicals including vital signs (HR, RR, BP), ECG, ECHO, and cardiac enzymes (Troponin and NT ProBNP) at protocol defined time points. Investigators should follow the guidelines in the protocol for detection and management of potential cardiac findings.

Renal Toxicity

Kidney findings were observed after chronic daily dosing only in the dog. In the current ongoing CLMI070X2201 study in Type 1 SMA no relevant renal adverse events have been identified. In the SAD and hADME studies in healthy subjects there have been no relevant abnormalities or changes in blood pressure, serum electrolyte levels or renal function variables or in the urinalysis assessments.

Other potential risks

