- Screening ECHO abnormalities per investigator's medical judgement including but not limited to left ventricular ejection fraction (LVEF) $<50\%$.
- Screening or baseline not within normal range Troponin or NTproBNP values.
- History or concomitant clinically significant cardiac arrhythmias (e.g., sustained ventricular tachycardia, atrial fibrillation, etc.), complete left bundle branch block, high-grade atrioventricular (AV) block (e.g., bifascicular block, Mobitz type II and third-degree AV block).
- History of familial long QT syndrome or known family history of Torsade de Pointes risks for TdP including uncorrected hypokalemia or hypomagnesemia, history of

clinically significant/symptomatic bradycardia and a family history of idiopathic sudden death.

- Resting QTcF ≥ 450 msec (male) or ≥ 460 msec (female) at pretreatment [screening or baseline] (as mean of triplicate ECGs), or inability to determine the QTcF interval.
- Use of agents known to prolong the QT interval or with a known or possible risk of Torsade de Pointes unless it can be permanently discontinued or replaced with a permitted medication (refer to [Table 6-2](#)).

15a. Uncontrolled hypertension (average 3 systolic blood pressure [SBP]readings) at screening >140 mmHg or average diastolic blood pressure [DBP] > 90 mmHg excluding values related to white coat syndrome (anxiety-related), per Investigator's judgement. Any clinically significant hematological abnormality as assessed by the Site Investigator at screening and/or laboratory evidence of any of the following:

- INR, PT, or activated partial thromboplastin time (APTT) that are not within normal ranges
- Hemoglobin <110 g/L (females) or <120 g/L (males)
- Platelets $\leq 100 \times 10^9$ /L
- Platelets count $>500 \times 10^9$ /L
- Neutrophil count $<1.5 \times 10^9$ /L
- Leukocytes $<3.0 \times 10^9$ /L

6 Treatment

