6.5.2.1 Dose adjustments for QTcF prolongation

As dose adjustments are not allowed, this section describes criteria for participant treatment interruption and permanent treatment discontinuation in case of QTcF prolongation. The Investigator should discontinue study treatment for a given participant if, on balance, he/she is of the opinion that continuation is not in the best interest of the participant or would be detrimental to the participant's well-being.

Clinically significant results or safety assessments that might put the participant at risk, including, but not limited to:

- Absolute QTcF >500 msec, confirmed by repeat ECG measurements
- Resting heart rate <30 or >120 bpm
- QRS >120 msec and increase >25% from Baseline
- Sustained ventricular tachycardia lasting 30 sec or more, ventricular fibrillation, or any hemodynamically compromising cardiac arrhythmia
- New complete heart block (Grade III AV block) or second-degree AV block Mobitz type II

In case of QTcF >500 msec (or QTcF prolongation >60 msec from baseline)

- Assess the quality of the ECG recording and the QT value and repeat if needed
- Interrupt study treatment
- Determine the serum electrolyte levels (in particular hypokalemia and hypomagnesemia). If abnormal, correct abnormalities before resuming study treatment.
- Review concomitant medication use for other causes for QT prolongation and for drugs with the potential to increase the risk of drug exposure related QT prolongation
- Check the dosing schedule and treatment compliance
- Consider collecting a time-matched PK sample and record time and date of last study treatment intake.

After confirming ECG reading at site, if QTcF >500 msec

- Interrupt study treatment
- Repeat ECG and confirm ECG diagnosis by a cardiologist or central ECG lab
- If QTcF confirmed >500 msec:

- Correct electrolytes, eliminate culprit concomitant treatments, and identify clinical conditions that could potentially prolong the QT as per the ECG and QTc Clinical Safety Standards Guidelines
- Consult with a cardiologist (or qualified specialist)
- Increase cardiac monitoring twice weekly until normalization or stabilization of the ECG findings, until the QTcF returns to ≤ 480 msec
- After resolution to ≤ 480 msec, consider permanent discontinuation of study drug treatment

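### SAP Table 5-10 measures QTcF change as ±20% from the previous visit, so it does not count the protocol's >60 ms prolongation from baseline

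*SAP*

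**What the plan says.** SAP Table 5-10 has two QTcF criteria. One is a level: below 320 or above 450 ms. The other, under "Notable relative change from previous visit", applies only to "QTcF Interval (Fridericia's correction") and is met at -20% or lower, or +20% or higher. In the same table the heart-rate change criterion is a "bpm change from baseline". The note that opens SAP Section 5.5 says that "in the below tables, we always used 'baseline' for clarity".

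Protocol Section 6.5.2.1 lists "Absolute QTcF >500 msec, confirmed by repeat ECG measurements" among the results that may put a participant at risk. It then gives a sequence of actions that begins "In case of QTcF >500 msec (or QTcF prolongation >60 msec from baseline"). Protocol Section 4.5, describing the healthy-volunteer study, reports outliers in categories: QTcF above 450 and 480 ms, and increases from baseline above 30 and 60 ms. The last of these reads "or QT from baseline > 60 ms and no ECG events".

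SAP Section 2.7.4.1 plans three ECG outputs: absolute values and change from baseline by visit and time point; the number and percentage of participants with newly occurring or worsening abnormalities; and a listing of participants with at least one abnormal value. Means of triplicates are already specified.

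**The concern.** The categorical table is where a reader looks for how many participants had a marked QTcF increase. Its change rule differs from the protocol's in reference point (previous visit instead of baseline) and in scale (percent instead of milliseconds). A rise spread over several visits is compared only with the visit before it. Table 5-10 also has no tier above 450 ms, so a small excess and a large one fall in the same category.

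Safety is one of the two primary objectives, and cardiovascular effects are a listed risk in Protocol Table 4-2. At stake is whether the report's outlier counts show the prolongation that the protocol itself singles out, and whether they can be compared with the healthy-volunteer study.

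**Working it through.** The plan gives no figure to reproduce; the check converts thresholds.

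**Inputs.** 20% from the previous visit and the limits of 320 and 450 ms (SAP Table 5-10); 60 ms from baseline and 500 ms (Protocol 6.5.2.1); entry limits (Protocol 5.2), which exclude QTcF of 450 ms or more in men and 460 ms or more in women "at pretreatment [screening or baseline] (as mean of triplicate ECGs), or inability to determine the QTcF interval". The range examined is 320 to 459 ms. The individual QTcF series below are assumed values.

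**1. The 20% rule in milliseconds.** The rise needed is 0.20 × previous QTcF. This equals 60 ms only at 60 / 0.20 = 300 ms. At 320 ms it is 64 ms and at 459 ms it is 91.8 ms. A 61 ms rise therefore never meets the rule anywhere in this range.

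**2. What the 450 ms flag adds.** A rise above 60 ms must end above 450 ms once the baseline is at least 450 - 60 = 390 ms. From there every such rise is flagged by level (for a baseline already above 450 ms, if a further rise counts as worsening).

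**3. Single-visit rises that meet neither rule.** These exceed 60 ms, are smaller than 0.20 × baseline, and do not exceed 450 - baseline.

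| Baseline (ms) | 20% step (ms) | 60 ms as % | 450 - baseline (ms) | Rises >60 ms with no QTcF flag |
|---|---|---|---|---|
| 320 | 64.0 | 18.8 | 130 | to just under 64 |
| 350 | 70.0 | 17.1 | 100 | to just under 70 |
| 360 | 72.0 | 16.7 | 90 | to just under 72 |
| 375 | 75.0 | 16.0 | 75 | to just under 75 |
| 380 | 76.0 | 15.8 | 70 | up to 70 |
| 389 | 77.8 | 15.4 | 61 | up to 61 |
| 390 | 78.0 | 15.4 | 60 | none |
| 400 | 80.0 | 15.0 | 50 | none |

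**4. Rises in steps.** If every step is below 20%, only the 450 ms limit applies, so a total rise of up to 450 - baseline has no flag (up to +100 ms from 350 ms).
- 370, 395, 420, 445 ms: the steps are 25/370 = 6.8%, 25/395 = 6.3% and 25/420 = 6.0%. The total is +75 ms and no value exceeds 450 ms, so there is no QTcF flag.
- 350 ms with +15 ms per visit: 440 ms after six visits, +90 ms, largest step 15/350 = 4.3%. The level flag appears only at the seventh visit (455 ms, +105 ms).

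**5. Severity above 450 ms.** A change from 440 to 451 ms (+11 ms) and one from 440 to 505 ms (+65 ms, 65/440 = 14.8%) fall in the same single category. The second meets both protocol criteria.

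**The case against.** The strongest reply is that most prolongation of interest is flagged somewhere. That stands in large part. Every value above 500 ms exceeds 450 ms. Every rise above 60 ms from a baseline of 390 ms or more ends above 450 ms. A rise from 400 ms, whether +60 ms at once (460 ms) or three steps of 25 ms (475 ms), is caught by level. Single-visit rises of 20% or more are caught by the change rule. A reader might infer that the SAP cannot detect a 60 ms rise or any gradual one, or that a value above 500 ms could go unreported; the documents do not support either reading.

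Change from baseline is also summarized by visit, and the default statistics in SAP Section 2.1 include the maximum, so a large individual rise could appear there. That stands, but a maximum per visit says neither how many participants were affected nor whether it is the same person at successive visits. The listing does not fill the gap: the 370 ms participant would be absent unless another ECG parameter was abnormal. Protocol Section 8.4.2 requires clinically significant ECG abnormalities to be recorded as medical history or adverse events; that depends on site judgement and is not a systematic count.

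A reader might also infer that the SAP contradicts a planned analysis. It does not. The 60 ms criterion in Protocol 6.5.2.1 is a treatment-interruption trigger, and Protocol 12.5.2 asks only for the number and percentage with clinically significant abnormalities. The Section 5.5 note mainly tells the reader to substitute the extension baseline in open-label summaries, so the previous-visit row departs from its wording without being a major conflict.

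Finally, the expected mean effect is small. The slope in Protocol 4.5 times the predicted Cmax at 56 mg in Protocol 4.2 gives 0.04912 × 40.8 = 2.0 ms. That lowers the priority, but outlier counts describe individuals, not means.

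**Conclusion.** The point stands as a reporting gap of modest weight. The only categorical QTcF change criterion needs about 64 to 92 ms between adjacent visits and ignores accumulation, so it does not count rises of more than 60 ms from baseline. Rises from baselines below 390 ms that end at or below 450 ms, with every step under 20%, escape every QTcF flag. From 390 ms upward they are flagged by level but not identified as a 60 ms change, and values above 480 or 500 ms are not separated.

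This rests on reading the table's abnormality flags as the basis for both the count and the listing, and on baselines within the 320 to 459 ms range. The documents do not give the baseline QTcF distribution, so the number of participants in the gap is unknown. Last dosing was on 08-Aug-2022, an abbreviated report is planned, and the analysis is descriptive, which limits the consequence. Nothing here bears on which clinical threshold should guide treatment.

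**What to change.** In SAP Table 5-10, replace the row on relative change from the previous visit with participant counts, by treatment group, of:
- maximum QTcF increase from baseline above 30 ms and above 60 ms;
- maximum post-baseline QTcF above 450, 480 and 500 ms.

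Use the triplicate means that SAP Section 2.7.4.1 already specifies, and let these categories also determine who enters the ECG listing. Say how participants already above 450 ms at baseline are counted, since women could enter at 451 to 459 ms and the SAP defines newly occurring and worsening only for laboratory values. The categories come from Protocol Sections 4.5 and 6.5.2.1; they serve reporting and set no treatment rule.

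The cost is one table edit and one summary table, from data already collected.
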